9.2.3.2 Exclusion Criteria

If at least one exclusion criterion is met, subject is not eligible for participation in the study, as follows:

- Enrolled in an interventional study of PCSK9 inhibitor within 12 weeks prior to initiation of Repatha®
- Received commercially available PCSK9 inhibitor within 12 weeks prior to initiation of Repatha®

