9.2.5 Baseline Period

The baseline period is from the 6 months prior to the first dose of Repatha® through to the date of administration of the first dose of Repatha®. Therefore, the end of the baseline period coincides with the first dose of Repatha®.

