9.3.2.1 Primary Outcome

Clinical characteristics at time of initiation of Repatha® as assessed in relation to:

- FH status (diagnosed/not diagnosed)
- CV history (see [Appendix B](#) for a list of diagnoses/events)

- Diabetic status (diabetic/not diabetic; Type 1 or Type II; HbA1C measurement closest to initiation of Repatha®)
- Cholesterol values including total cholesterol, LDL-C, HDL-C, non-HDL-C, triglycerides (value(s) available in the 26-week baseline period)
- Demographics (age at initiation of Repatha®, gender, country)
- Cardiovascular risk factors (body mass index (BMI), smoking status, chronic kidney disease, history of hypertension, vascular bed involvement (see also [Appendix B](#)))
- History of statin intolerance (y,n)
- Dose, dose frequency, commencement date of Repatha® administration
- Type, dose, dose frequency, commencement and discontinuation dates of other LMT administration including apheresis
- Dates and reason for hospital admittance/final diagnosis
- Dates of physician visits and reason for attendance

Of note, LMT use (including apheresis) over the 6 months prior to initiation of Repatha® will be summarised and the regimen in place at the time of Repatha® initiation will be regarded as the baseline.

In addition, LDL-C and other relevant lipid panel measurements and HbA1C as assessed within 6 months prior to initiation of Repatha® (or the mean of the two most recent LDL-C measurements, if there is more than one) will be regarded as the respective baseline values.

All CV history and diabetic status will be reported as baseline data

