9.7.2 Planned Method of Analysis

All summaries of the data will be descriptive in nature. For categorical variables the frequency and percentage, with 95% confidence interval, will be given.

Summary statistics for continuous variables will include the number of subjects, mean, median, standard deviation or standard error, 25th percentile (Q1), 75th percentile (Q3), minimum, and maximum.

For the outcome measure of LDL-C and other cholesterol values over time, the data collection period (up to 6 months pre-initiation of Repatha® and up to 30 months post-initiation of Repatha®) will be divided into time windows. For each subject the mean LDL-C and other cholesterol values during each time period will be obtained, and summary statistics will be produced based on these mean values. In order to optimally utilize the available LDL-C and other cholesterol data, the following time windows will be used:

Definition 1: Period of 6 months duration pre-initiation of Repatha® (to obtain baseline LDL-C), windows of 3 months duration post initiation of Repatha® (months 1-3, months 4-6, months 7-9 and so on, through months 28-30)

Definition 2: Period of 6 months duration pre-initiation of Repatha® (to obtain baseline LDL-C), windows of 6 months duration post initiation of Repatha® (months 1-6, months 7-12, months 13-18 and so on through months 25-30)

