9.9 Limitations of the Research Methods

9.9.1 Internal Validity of Study Design

9.9.1.1 Information Bias

For the primary objective, information bias is not anticipated to be applicable, as Investigators will be aware of the subjects' age and gender, and will have paid particular attention to their CV history as they have been referred for CV cause. It is possible that lipids may be measured more frequently in very high risk and/or sicker patients, which could influence the baseline LDL-C; to help prevent this, a maximum of two LDL-C values in the 6 months prior to initiation of Repatha® will be considered for inclusion in the baseline, and these will be the two most recent values prior to the initiation date.

For the secondary objectives, it is expected that Investigators will follow all subjects closely as: 1. they have been initiated on a novel therapeutic in the immediate post-launch period. LDL-C values and use of Repatha® and any concomitant medications will be significant markers of clinical care, and are likely to be assessed on an ongoing basis over the observation period. 2. Subjects are high risk patients in secondary care.

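### PCSK9-inhibitor use is excluded for only 12 weeks while baseline LDL-C looks back 26 weeks, so a few baseline values may have been drawn on a drug of the same class

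*Protocol*

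**What the plan says.** Section 9.2.3.2 (Exclusion Criteria) has two bullets on earlier PCSK9-inhibitor use. One covers marketed product: "Received commercially available PCSK9 inhibitor within 12 weeks prior to initiation of Repatha". The other covers trials: "Enrolled in an interventional study of PCSK9 inhibitor within 12 weeks prior to initiation of Repatha". Both reach back 12 weeks.

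The baseline window is longer. Section 9.2.5: "The baseline period is from the 6 months prior to the first dose of Repatha® through to the date of administration of the first dose". Section 9.3.2.1 describes the lipid values in the primary outcome as "value(s) available in the 26-week baseline period". The baseline value is the measurement in that window "or the mean of the two most recent LDL-C measurements, if there is more than one) will be regarded as the respective baseline values". Section 9.9.1.1 repeats the limit: "a maximum of two LDL-C values in the 6 months prior to initiation of Repatha® will be considered for inclusion in the baseline". For LDL-C over time, Section 9.7.2 defines the first window as "Period of 6 months duration pre-initiation of Repatha® (to obtain baseline LDL-C" and summarises each subject by the mean of the values within a window.

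None of these sections makes a baseline value depend on whether the subject was on a PCSK9 inhibitor when the blood was drawn. Section 9.3.2.1 also takes the lipid-modifying regimen current at Repatha initiation as the baseline regimen.

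**The concern.** An eligibility rule and a measurement rule are both fixed in the protocol, and between them they leave an interval that neither covers. A subject who stopped a PCSK9 inhibitor in that interval enters the study, and an LDL-C drawn before stopping qualifies as a baseline value. The subject is then recorded with a baseline regimen that contains no PCSK9 inhibitor, next to an LDL-C measured on one.

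Section 9.5 names mean LDL-C before initiation as the continuous primary outcome measure, and Section 9.7.2.5.1 splits subjects at its median. An on-drug value pulls a subject's baseline in one direction only, downward, and can put the subject in the below-median group. The confidence interval does not reflect an error of this kind.

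**Working it through.** **1. The plan's own precision figure.** Half-width = 1.96 × SD / √N. With SD 50 mg/dL and N = 130 (Section 9.5): 1.96 × 50 / √130 = 8.60 mg/dL, as stated. All 16 cells of the table reproduce to within 0.01.

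**2. The uncovered interval.** Look-back 26 weeks (Section 9.3.2.1), exclusion 12 weeks (Section 9.2.3.2): 26 − 12 = 14 weeks, and 14 / 26 = 54% of the look-back.

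**3. Who is affected.** Under Sections 9.3.2.1 and 9.9.1.1 only the two most recent values count. A subject is affected only if a PCSK9 inhibitor was stopped in the uncovered interval and fewer than two LDL-C values were taken afterwards.

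Section 9.7.2, read literally, averages every value in the six-month window. Take a hypothetical subject with LDL-C 75 on drug and 150 off drug, who stopped at week −13 and was measured at weeks −24, −18, −8 and −2:
- Two most recent values: (150 + 150) / 2 = 150.
- All values in the window: (75 + 75 + 150 + 150) / 4 = 112.5.

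The same subject would have two different baselines, and only the second contains on-drug values.

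**4. Size.** The documents give neither the share of such subjects nor the LDL-C lowering, so the following are assumptions: off-drug mean m = 120 to 180 mg/dL; lowering r = 50 to 60%; weight of on-drug values in the subject's baseline w = 0.5 (one of two) or 1 (all); share of subjects affected f = 1, 5 or 10%.

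Error in one subject = w × r × m:
- w = 1: 0.5 × 120 = 60 up to 0.6 × 180 = 108 mg/dL too low.
- w = 0.5: 30 to 54 mg/dL too low.

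Shift in a country mean = f × w × r × m:

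| f | subjects of 130 | lowest (w 0.5, r 0.5, m 120) | highest (w 1, r 0.6, m 180) |
|---|---|---|---|
| 1% | 1.3 | 0.3 | 1.1 |
| 5% | 6.5 | 1.5 | 5.4 |
| 10% | 13 | 3.0 | 10.8 |

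**5. Share needed to equal the half-width.** f = 8.60 / (w × r × m):
- w = 1: 8.60 / 108 = 8% to 8.60 / 60 = 14%.
- w = 0.5: 8.60 / 54 = 16% to 8.60 / 30 = 29%.

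**The case against.** The best reply is that nothing is contradictory. The 12 weeks govern who may enter, the 26 weeks govern how far back the chart is read, and no section says that they must match. The outcome is LDL-C before Repatha, on whatever therapy the subject then had, and Section 9.7.2.3.2 wants the criteria to be inclusive. The two-most-recent rule already favours values close to initiation. Dates of other lipid-modifying therapy are collected, so recorded exposure can be traced, and the statistical analysis plan, which is not at hand, may handle individual values.

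Much of this stands. The mismatch is a gap rather than a contradiction, and the two-most-recent rule narrows it. What remains is that the protocol itself fixes the selection of baseline values, and following it exactly admits an on-drug value. Section 9.9.1.1 already restricts which values count in order to protect this outcome, so a further condition is in keeping with the plan.

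A reader might infer more than the documents support:
- **That many subjects are affected, because former trial participants gather at specialist sites.** Section 9.2.2 says that the sites are specialist and treat high-risk patients. It says nothing of earlier trial participation. The 5% and 10% rows above only illustrate scale.
- **That the fall in LDL-C on Repatha will be underestimated.** Sections 9.7.2 and 9.7.2.4.2 plan summaries per time window and state no change-from-baseline estimate. Only an informal comparison of windows would be touched.
- **That every value up to 12 weeks after the last dose should be dropped.** For a subject who stopped at week −13 this would discard all values through week −1, including those nearest to initiation, and could leave the baseline missing although off-drug values exist.

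**Conclusion.** The point holds in a limited form. Subjects who stopped a PCSK9 inhibitor more than 12 but less than 26 weeks before Repatha are eligible, and the baseline rule does not prevent an on-drug LDL-C from being their only baseline value or one of those averaged. For such a subject the baseline could be too low by 30 to 108 mg/dL under the stated assumptions, and the median-split group could be wrong.

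For a country mean the effect is probably small: 0.3 to 1.1 mg/dL at 1% affected. It matches the planned half-width of 8.60 only at 8 to 14% affected with every value on drug, or 16 to 29% with one of two. The documents do not allow the true share to be estimated. Sample size and the precision table are not in question. The case for acting is that the error has one direction, concerns the primary outcome and is cheap to remove or display.

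Two related wordings add uncertainty. Section 9.7.2, taken literally, admits more on-drug values than Section 9.3.2.1. The trial exclusion turns on enrolment rather than last dose, so it is unclear how it treats a subject who enrolled earlier but was still being dosed within the 12 weeks; the bullet on marketed product does not cover trial drug.

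**What to change.** Leave eligibility as it is and change the handling of values:

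1. In Section 9.3.2.1, state that lipid values drawn between the recorded start and stop dates of a prior PCSK9 inhibitor are not used for baseline when a later off-drug value exists in the window.
2. Flag every subject with PCSK9-inhibitor exposure, commercial or trial, in weeks −26 to −12. Report their number and present baseline LDL-C with and without them. This also shows the effect of subjects whose only value is on drug, whom step 1 leaves in, and of any lowering that persists after stopping.
3. In Section 9.7.2, use the same baseline rule for the pre-initiation window, so that the protocol has one baseline LDL-C.
4. Confirm that the eCRF captures prior PCSK9-inhibitor dates, including trial drug where known. Section 9.3.2.1 and Appendix C provide for other lipid-modifying therapy but do not say that investigational product is entered there. Clarify how the trial bullet in Section 9.2.3.2 treats earlier enrolment with continued dosing.

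The cost is a little extra programming and a slightly smaller N in the summary that leaves the flagged subjects out. No subject loses a baseline value in the main summary, because an on-drug value is set aside only when a later off-drug one can replace it. Where trial dates or allocation are unknown to the site, the flag will be incomplete, and the report should say so.

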9.2.4 Matching

NA

9.2.5 Baseline Period

The baseline period is from the 6 months prior to the first dose of Repatha® through to the date of administration of the first dose of Repatha®. Therefore, the end of the baseline period coincides with the first dose of Repatha®.

9.2.6 Study Follow-up

Follow-up of each subject will be for 30 months after date of first administration of Repatha®, death, withdrawal of consent or loss to follow-up (whichever occurs earliest). Subjects will be followed regardless of continuation/discontinuation of Repatha®, including for subjects who received only one dose of Repatha®.

If subjects are lost to follow-up, the site will be encouraged to confirm the reason, which may include withdrawal of consent or relocation to a different physician.

Study duration is considered sufficient to allow an estimation of Repatha® and other LMT usage and LDL-C concentrations over time, following initiation of Repatha®.

9.3 Variables

9.3.1 Exposure Assessment

Exposure to Repatha® and other LMT will be assessed through review of medical charts.

9.3.2 Outcome Assessment

Outcome measures reflect parameters used in routine clinical management, and are expected to provide data which are of interest to physicians and health authorities, as these measures are directly relevant to current clinical practice.

To provide baseline information for each subject, in addition to demographic data (age, gender, country) and established cardiovascular risk factors (BMI, hypertension, CKD, smoking status, vascular bed involvement), data on other key variables will also be collected such as history of statin intolerance and also current aspirin use. For an overview which assessments are recorded into an electronic case report form (eCRF) at which points in a subject's observation period, please also refer to [Appendix C](#).

9.3.2.1 Primary Outcome

Clinical characteristics at time of initiation of Repatha® as assessed in relation to:

- FH status (diagnosed/not diagnosed)
- CV history (see [Appendix B](#) for a list of diagnoses/events)

- Diabetic status (diabetic/not diabetic; Type 1 or Type II; HbA1C measurement closest to initiation of Repatha®)
- Cholesterol values including total cholesterol, LDL-C, HDL-C, non-HDL-C, triglycerides (value(s) available in the 26-week baseline period)
- Demographics (age at initiation of Repatha®, gender, country)
- Cardiovascular risk factors (body mass index (BMI), smoking status, chronic kidney disease, history of hypertension, vascular bed involvement (see also [Appendix B](#)))
- History of statin intolerance (y,n)
- Dose, dose frequency, commencement date of Repatha® administration
- Type, dose, dose frequency, commencement and discontinuation dates of other LMT administration including apheresis
- Dates and reason for hospital admittance/final diagnosis
- Dates of physician visits and reason for attendance

Of note, LMT use (including apheresis) over the 6 months prior to initiation of Repatha® will be summarised and the regimen in place at the time of Repatha® initiation will be regarded as the baseline.

In addition, LDL-C and other relevant lipid panel measurements and HbA1C as assessed within 6 months prior to initiation of Repatha® (or the mean of the two most recent LDL-C measurements, if there is more than one) will be regarded as the respective baseline values.

All CV history and diabetic status will be reported as baseline data

9.3.2.2 Secondary Outcomes

- Age at initiation of Repatha®
- Gender
- Country of residence
- Relevant laboratory measures including LDL-C, other test results of the lipid panel (over time; values available during the 30-month follow-up period)
- Use of Repatha® (at initiation of Repatha® and during the 30-month follow-up period; type, dose, frequency, switching)
- LMTs (over the full observation period (ie, from baseline throughout the 30-month follow-up period); type, dose, frequency, switching)
- Medication persistence
- Medication adherence
- Incidence of hospitalisation (dates, including reason for admittance/final diagnosis)
- Incidence of physician visits (dates, including reason for attendance)

9.3.2.3 Exploratory Outcome

- Incidence of LDL-C < 50 mg/dL (< 1.3 mmol/L)

9.3.3 Covariate Assessment

NA

9.3.4 Validity and Reliability

Study variables stated in this protocol are objective, relevant to the question under study and are accepted as appropriate by regulatory authorities. Variables to be evaluated in the study are parameters which are routinely measured as part of clinical management of patients with hyperlipidaemia.

Data for this non-interventional, observational study are collected through serial review of subjects' charts. Clinical management of enrolled subjects will not be altered through the study protocol. Therefore, data from subjects' medical records is expected to be valid and reliable in reflecting their routine clinical management.

9.4 Data Sources

Study site staff will abstract data from subject medical notes and enter these into eCRF pages of the sponsor's electronic database. Sites participating in the study will be fully trained by Amgen in data entry and use of the study-specific database and eCRFs.

Chart reviews and data abstraction will be conducted periodically (at a minimum 3-monthly). Data capture comprises the baseline and follow-up periods as described in [Section 9.2.5](#) and [Section 9.2.6](#), respectively.

[figure not shown]
The first data abstraction into the CRF should occur as soon as the patient is enrolled into the study.

The periodic data abstractions are expected to occur once every 3 months thereafter.

9.5 Study Size

The primary outcome measures for the study involve estimating the percentage of subjects with clinical characteristics of interest (FH, CV history, diabetes - yes or no for each outcome measure) and also estimating the baseline LDL-C levels. The intention is to perform the analyses by country. The planned sample size for the study is 2000 subjects across approximately 15 countries; an average of approximately 130 subjects per country. The figure below shows the expected precision of estimates of the binary outcome measures for a range of sample sizes above and below 130 and for a range of percentages of subjects with and without the conditions of interest. This

gives an indication of the likely precision of estimates and demonstrates that the sample size per country will enable sufficiently precise estimates to be obtained for the primary outcome measures. For example, with a sample size of 130 in the country and assuming 35% of subjects have the condition being summarised, the ½ width of the 95% confidence interval around the estimate would be approximately 8%.

The table below shows the estimated precision of the continuous primary outcome measure, the mean LDL-C value prior to initiation of Repatha®, assuming a range of sample sizes and standard deviations (standard deviations based on those observed in phase 3 studies).

Standard deviation	½ width of 95% CI in mg/dL			
	N = 70	N = 100	N = 130	N = 150
40	9.37	7.84	6.88	6.40
45	10.54	8.82	7.74	7.20
50	11.71	9.80	8.60	8.00
55	12.89	10.78	9.46	8.80

The sample size will also enable the secondary outcome measures to be precisely estimated. This includes the LDL-C over time after initiation of Repatha, after allowing for missing data due to subject withdrawal (expected to be up to 10% per year over the 30 months follow-up period).

9.6 Data Management

Data are abstracted by site staff from subject notes into an electronic database provided by the sponsor. The sponsor provides protocol-specific training to all site staff delegated to abstract subject data.

The Amgen representative(s) and regulatory authority inspectors are responsible for contacting and visiting the Investigator for the purpose of inspecting the facilities and, upon request, inspecting the various records of the clinical study (eg, CRFs and other pertinent data) provided that subject confidentiality is respected.

The Clinical Monitor or designee is responsible for verifying the CRFs at regular intervals throughout the study to verify adherence to the protocol completeness, accuracy, and consistency of the data; and adherence to local regulations on the conduct of research. The Clinical Monitor, or designee is to have access to subject medical records and other study-related records needed to verify the entries on the CRFs in accordance with the local laws and regulations.

The Investigator agrees to cooperate with the Clinical Monitor, or designee to ensure that any problems detected in the course of these monitoring visits, including delays in completing CRFs, are resolved.

In accordance with the sponsor's audit plans, this study may be selected for audit by representatives from Amgen's Global Compliance Auditing function (or designees). Review of study-related records will occur to evaluate the study conduct and compliance with the protocol, and applicable regulatory requirements.

Data capture for this study is planned to be electronic:

- All source documentation supporting entries into the electronic CRFs must be maintained and available upon request.
- Updates to electronic CRFs will be automatically documented through the software's "audit trail".

- To ensure the quality of clinical data across all subjects and sites, a clinical data management review is performed on subject data received at Amgen. During this review, subject data is checked for consistency, omissions, and any apparent discrepancies. To resolve any questions arising from the clinical data management review process, data queries are created in the EDC system database for site resolution and closed by Amgen reviewer.
- The Investigator **applies an electronic signature in the electronic data capture (EDC) database. This signature indicates that investigator inspected or reviewed the data on the CRF, the data queries, and agrees with the content.**

9.6.1 Obtaining Data Files

NA

9.6.2 Linking Data Files

NA

9.6.3 Review and Verification of Data Quality

Automatic edit checks within the database and further manual review by the sponsor help to ensure quality and completeness of the data. Data queries are sent to site for clarification and resolution of discrepancies.

9.7 Data Analysis

9.7.1 Planned Analyses

9.7.1.1 Interim Analyses

Interim analyses (IAs) will be performed according to individual country need, where possible, to provide a timely snapshot of essential data prior to the final analysis (see also [Section 6](#)). Country-specific analyses will be provided at the interim analysis stage where possible, according to enrolment and duration of follow-up (for some countries baseline data only may be presented at the interim analyses).

